## **Objectives:**

1. To evaluate the effect of cryoneurolysis on pain in patients with hand and wrist contracture.
2. To assess any changes in wrist and fingers ROM and spasticity in patients with hand and wrist contracture.
3. To evaluate if there is any correlation between changes in ROM and spasticity with pain
4. To record any changes in pain medication that they receive for pain management.

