## **Research Design:**

This project constitutes a single-centre, prospective cohort study. Data collection will occur at the Victoria General Hospital (VGH) spasticity clinic. Patients with severe spasticity and contracture are referred to this clinic for different procedures including cryoneurolysis. This study will not interfere or change the patients' medical care. We will do the assessments for the patients who are already candidates for this procedure as a

Effect of the cryoneurolysis on pain and positioning in patients with wrist and hand contracture. 4

Protocol: [H22-03181]

Version 1.1

Jan 9,2023

part of their treatment, besides other provided medical cares and have been accepted to receive it.

All measurements are a part of routine assessment for patients with severe spasticity and contracture.

The evaluation will be done for them after receiving oral and written consent.

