### **Methods:**

The assessment will be done at baseline, 2 weeks, 1 month and 3 months after being enrolled in the study in the same day of their appointments with [name] and includes;

1. Passive and any active range of motions (ROM) of wrist, second and fifth MCP and PIP joints and thumb palmar and radial abduction will be measured by goniometer. Spasticity will be measured based on Modified Ashworth Scale (MAS).
2. The maximum distance between the pulp of the most flexed finger and thumb and the palm of the hand will be measured in centimeter. This distance will be measured during maximal passive extension of the fingers and thumb while the assessor keep the wrist in neutral (or as close to neutral as possible )position.
3. Intensity of pain in the wrist and hand area will be measured by NRS (numerical rating scale), for patients with sufficient cognitive capacity. In this test patients will be asked to score their pain on scale of 0 to 10. Patients who cognitively are not able to score their pain will be assessed by CNPI scale (Checklist of Nonverbal Pain Indicators). In this scale the patient will be observed at rest and during any movement and any nonverbal vocal complaints, facial grimaces, bracing, restlessness, rubbing of the affected area and verbal vocal complaints will be scored accordingly. PI will decide which one of these 2 methods is applicable, based on their assessments, patients' record and in consult with their caregivers.
4. Goal Attainment Scale (GAS): This is a patient-oriented scale to deliver the patient their desired outcomes. Up to 3 individualized, SMART (specific, measurable, achievable, realistic and timed ) goals will be negotiated between participants, caregivers and their physician. At the final visit, they will be asked if they are satisfied with each of these goals and the response will be scored accordingly.

Effect of the cryoneurolysis on pain and positioning in patients with wrist and hand contracture. 5

Protocol: [H22-03181]

Version 1.1

Jan 9,2023

5. Hand hygiene: the evaluator will assess the patients' hands to determine the extent of palm maceration, ulceration or infection; cleanliness of the palm, ease of cleaning and nail trimming; and the effect of hygiene-related disability on other areas of functioning. This assessment is a part of disability assessment scale (DAS). The score ranges from 0 to 3 based on the severity of the maintaining the hand hygiene.

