### **Statistical Analysis:**

A convenience sample of  $n = 25$  patients will be included in this study. This is consistent with existing volumes of consultations to our clinics. Study recruitment will include all patients with wrist and hand contracture that are considered for cryoneurolysis. The outcome measures that we will use are standard clinical measures, but effect sizes are not readily available from previous studies to formally calculate sample size. Furthermore, our study uses an exploratory prospective cohort design, rather than a parallel group trial design, limiting the rationale for providing a sample size calculation.

To assess for statistical significance, a paired t-test on the difference of proportions, applicable to pre-treatment and post-treatment, will be performed. We will employ repeated measures or linear mixed (multilevel) models of change to analyze within-person trajectories in all key outcomes for the intensive repeated measures data spanning the 4-month study period. Such models derive individual parameter estimates for baseline function and change pursuant to nerve or surgical procedure and will directly index the magnitude in improvement for each outcome with everyone serving as their own control (i.e., with change indexed relative to everyone's own personal baseline). If normal distribution in the outcomes does not stand, McNemar's test and

Spearman correlations will be calculated instead of paired t-test and Pearson's correlation, respectively.

The correlation between range of motion and pain score will be reviewed by Pearson's correlation and or Spearman's rank correlation at single time point. The improvement of range of motion or pain scores during two visits will be compared by two sample t test or Wilcoxon rank sum test.

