**Inclusion criteria:**

1. Adult patients(at least 18 years old).
2. Severe claw hand with less than 4 cm distance between the pulp of the fingers and palm of the hand.
3. MAS $\geq$  3 in wrist and hand muscles interfering with function or causing a clinical problem, due to any neurological condition.
4. Have refractory pain in wrist and hand area with no response to the usual pain management methods including oral medication or botulinum toxin injection.
5. Patients are already candidate for cryoneurolysis for pain and spasticity in their hand and wrist, based on their response to DNB.
6. Ability to attend testing sessions, comply with testing protocols and provide written informed consent. For patients who physically are not able to complete the consent process, a witness may be asked to sign and confirm their willing for participation. Legal representative may be asked to help with consent process for participants who cognitively are not able to consent on their behalf.

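### Pain is measured on one of two scales by cognition, but the analysis section names a single pain score; say that NRS and CNPI values are kept apart

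*Protocol*

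**What the plan says.** Methods, item 3, sets out two pain measures. Patients with sufficient cognitive capacity rate their pain from 0 to 10 on the NRS. For the rest, "Patients who cognitively are not able to score their pain will be assessed by CNPI scale (Checklist of Nonverbal Pain Indicators", which an observer scores at rest and during movement. The choice is the investigator's: "PI will decide which one of these 2 methods is applicable, based on their assessments", together with records and caregivers' views. The score range of the CNPI is not given.

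Both kinds of patient can enrol. Inclusion criterion 6 provides that "Legal representative may be asked to help with consent process for participants who cognitively are not able to consent on their behalf", and Recruitment, item d, expects many participants from long-term care.

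The Statistical Analysis section names neither instrument. It says "The correlation between range of motion and pain score will be reviewed by" Pearson's or Spearman's "rank correlation at single time point", and "The improvement of range of motion or pain scores during two visits will be compared by two sample t test" or a rank-sum test. It also plans repeated-measures or mixed models for all key outcomes, with each patient's change taken from that patient's own baseline.

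**The concern.** An NRS point is a patient's own rating. A CNPI point is something an observer saw. Nothing in the protocol places the two on a common scale, and patients are sorted between them by cognition, which may go with differences in ROM. A correlation across all patients at one visit therefore contains two parts: the relation within each instrument, and the difference between the two groups in score level and in ROM. The second part says nothing about whether pain goes with stiffness.

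Pain is objective 1. The relation of pain to ROM and spasticity is objective 3, and hypothesis 3 holds that pain reduction is independent of both. A correlation weakened by the scale mix could be taken as support for independence, and one created by the mix as evidence against it. A pooled mean change raises a different problem: its value depends on how many patients were on each scale, even when the treatment effect is the same.

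**Working it through.** The protocol has no figure to reproduce. Its n = 25 is a convenience sample, with no SD, effect size, CNPI share or CNPI range. Everything below except n = 25 is assumed and serves only to show the direction and range of the effect.

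**Pooled correlation.** Let p be the CNPI share, s1 and s2 the NRS and CNPI SDs, D the CNPI mean minus the NRS mean, E the ROM mean difference (CNPI minus NRS) in SD units, and rho the correlation within each instrument. Then

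pooled r = [rho((1−p)s1 + p·s2) + p(1−p)DE] / √{[(1−p)s1² + p·s2² + p(1−p)D²]·[1 + p(1−p)E²]}.

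Worked case: p = 0.4 (10 of 25), s1 = s2 = 2, D = −3, E = 0, rho = −0.5. The numerator is −0.5 × 2 = −1. The denominator is √(4 + 0.24 × 9) = √6.16 = 2.48. So r = −0.40.

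| rho | D | E = −1 | −0.5 | 0 | +0.5 | +1 |
|---|---|---|---|---|---|---|
| −0.5 | −3 | −0.10 | −0.25 | −0.40 | −0.53 | −0.62 |
| −0.5 | −1.5 | −0.27 | −0.37 | −0.47 | −0.54 | −0.57 |
| 0 | −3 | +0.26 | +0.14 | 0 | −0.14 | −0.26 |

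A score gap alone weakens the correlation. A score gap together with a ROM gap can weaken, strengthen or create it.

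**Test behaviour** (simulation, 15 + 10 patients, normal data, two-sided 5%, 100,000 runs). With rho = 0, the pooled Pearson test rejects as follows:

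| Score gap | ROM equal | 0.5 SD apart | 1 SD apart |
|---|---|---|---|
| 1.5 points | 5% | 7% | 11% |
| 3 points | 5% | 11% | 26% |

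A repeat with another seed gave 10% and 25% in the last two cells of the 3-point row. A test stratified by instrument (Fisher z, weights n−3) rejects in 5% throughout. With rho = −0.5 and equal ROM, pooled versus stratified power is 0.52 versus 0.71 (3-point gap), 0.68 versus 0.71 (1.5-point gap) and 0.75 versus 0.71 (no gap).

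**Does Spearman help?** No. A second simulation (3,000 runs) used a CNPI share of 40%, the same relative pain in both groups (mean 70%, SD 20% of each scale's maximum), ROM SD 15 degrees, ROM 15 degrees lower in CNPI patients, and no true correlation. Rejection was 30% for Pearson and 31% for Spearman if the CNPI maximum is 6, and 10% and 9% if it is 12.

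**Changes.** If each patient stays on one scale, a constant offset between scales cancels. Take p = 0.4, s1 = 2 and rho = −0.5. With equal mean changes in pain and in ROM, pooled r is −0.48 (s2 = 1) or −0.50 (s2 = 2). If mean pain change differs by 0.6 points and ROM change by up to 1 SD, it runs from −0.35 to −0.52.

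**Pooled mean change.** Suppose pain falls by 0.6 SD on each scale: 1.2 points on the NRS (SD 2) and 0.6 on the CNPI (SD 1). With 40% on CNPI the mean is 0.6 × (−1.2) + 0.4 × (−0.6) = −0.96. With 20% it is 0.8 × (−1.2) + 0.2 × (−0.6) = −1.08. The effect is the same but the figure is not.

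**The case against.** The best defence is that the fault is read from silence. The section never says that NRS and CNPI values are combined. Its models for all key outcomes would equally fit two separate pain outcomes, and an analysis plan not shown here may split them. A reader might infer that pooling is planned, but the text does not establish that. What stands is narrower: the protocol itself creates two scales and then specifies a correlation on one undivided score.

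A reader might also infer that a patient may change scale between visits. The wording on the investigator's choice reads more naturally as one decision per patient. Retention over visits is merely unstated, and one line would confirm it.

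The own-control argument is right for a patient's change and is the reason correlations of changes suffer little. It does not help the single-visit correlation, where no baseline is subtracted, and it does not give a mean over two scales a unit.

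The figures are all assumed, and the 3-point gap is the harsh case. Marked distortion needs a sizeable score gap and a sizeable ROM gap together. With an assumed CNPI maximum of 12, a true −0.50 appears as −0.47 to −0.56, which is little distortion.

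Finally, objective 3 is "To evaluate if there is any correlation between changes in ROM and spasticity with pain", whereas the correlation that is specified is cross-sectional. That mismatch would exist with one pain scale too, so it adds no weight here.

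**Conclusion.** The point holds in a limited form. As worded, the single-time-point pain-ROM correlation puts two non-interchangeable scales into one coefficient, and a pooled mean pain change has no clear unit. Neither ranking nor own-baseline change cures both.

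Neither the direction nor the size of any distortion can be derived from the protocol. Under the assumed 15 + 10 split and SD 2, the false-positive rate ranges from about 5% (equal ROM) to about 11% or 26% (1 SD ROM difference, with a 1.5- or 3-point gap). These figures show exposure and are not a forecast. They do not support a claim that the pain results will be invalid: within-patient change on a retained scale remains interpretable.

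For an exploratory pilot of 25 with no power claim, this is a minor matter and a cheap improvement.

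**What to change.** **Statistical Analysis.** State that raw NRS and CNPI values are not combined. Report pain levels, changes and the repeated-measures or mixed model separately for each instrument. Compute pain-ROM correlations within instrument, and list the individual values where a group is too small for a coefficient.

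If one overall test of pain change is wanted, use a signed-rank test stratified by instrument, so that all 25 patients contribute. A combined correlation is optional. It should be Pearson-based and used only with adequate strata, because Fisher-z weighting by n−3 gives no weight to a stratum of three and is undefined if a very small stratum yields a Spearman coefficient of exactly ±1.

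**Methods, item 3.** Confirm that the instrument chosen for a patient is kept at all visits.

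**Cost.** A few sentences and no new assessments, which fits the Research Design statement that "All measurements are a part of routine assessment for patients with severe spasticity and contracture". The price is precision within instrument. Around r = −0.50, the 95% interval is −0.81 to +0.02 for n = 15 and −0.86 to +0.19 for n = 10, against −0.75 to −0.13 if all 25 shared one scale. If the scales do not in fact differ, a stratified correlation loses a little power (about 0.75 to 0.71). For overall change with a 0.6 SD shift, stratified signed-rank power is 0.79 against 0.80 on one scale. If the CNPI effect is half as large in SD units (CNPI SD 1, NRS SD 2), it is 0.59 against 0.62 for a raw pooled test.

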### **Statistical Analysis:**

A convenience sample of  $n = 25$  patients will be included in this study. This is consistent with existing volumes of consultations to our clinics. Study recruitment will include all patients with wrist and hand contracture that are considered for cryoneurolysis. The outcome measures that we will use are standard clinical measures, but effect sizes are not readily available from previous studies to formally calculate sample size. Furthermore, our study uses an exploratory prospective cohort design, rather than a parallel group trial design, limiting the rationale for providing a sample size calculation.

To assess for statistical significance, a paired t-test on the difference of proportions, applicable to pre-treatment and post-treatment, will be performed. We will employ repeated measures or linear mixed (multilevel) models of change to analyze within-person trajectories in all key outcomes for the intensive repeated measures data spanning the 4-month study period. Such models derive individual parameter estimates for baseline function and change pursuant to nerve or surgical procedure and will directly index the magnitude in improvement for each outcome with everyone serving as their own control (i.e., with change indexed relative to everyone's own personal baseline). If normal distribution in the outcomes does not stand, McNemar's test and

Spearman correlations will be calculated instead of paired t-test and Pearson's correlation, respectively.

The correlation between range of motion and pain score will be reviewed by Pearson's correlation and or Spearman's rank correlation at single time point. The improvement of range of motion or pain scores during two visits will be compared by two sample t test or Wilcoxon rank sum test.

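### The pre/post test is written for paired yes/no data that the protocol never defines, and a conflicting unpaired rule is added for pain and range of motion

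*Protocol*

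**What the plan says.** The Statistical Analysis section of the protocol gives three rules for change between visits.

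- **Pre/post significance test.** It states that "a paired t-test on the difference of proportions, applicable to pre-treatment and post-treatment, will be performed". The fallback sentence begins "If normal distribution in the outcomes does not stand, McNemar's test and" and continues "Spearman correlations will be calculated instead of paired t-test and Pearson's correlation, respectively". The closing word of that sentence pairs McNemar's test with the paired t-test, and Spearman with Pearson.
- **Repeated measures or linear mixed models** for all key outcomes, "with everyone serving as their own control".
- **A further rule for range of motion and pain**, in the last sentence: "pain scores during two visits will be compared by two sample t test or Wilcoxon rank sum test".

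The Methods section defines the outcomes. For pain, "In this test patients will be asked to score their pain on scale of 0 to 10"; patients who cannot do this are scored on the CNPI. For hand hygiene, "The score ranges from 0 to 3 based on the severity of the maintaining the hand hygiene". For goal attainment, "At the final visit, they will be asked if they are satisfied with each of these goals".

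**The concern.** A paired t-test compares means of within-patient numerical differences. McNemar's test compares paired yes/no results. Non-normality of a score does not turn it into a yes/no outcome, so McNemar's test is not the distribution-free counterpart of the paired t-test. That counterpart is the Wilcoxon signed-rank test, which the section does not name.

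The two-sample t-test and the rank sum test assume independent groups. Here the two samples would be two visits of the same patients. For non-normal pain scores the section therefore points to McNemar's test in one place and to the rank sum test in another, and neither suits paired scores.

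Two things are at stake. An analyst who follows the McNemar route must split each score at a cut-off that could be picked after seeing the data, and loses information by doing so. An analyst who follows the last sentence discards the pairing. Pain and range of motion are the subjects of Objectives 1 and 2, so the conflict falls on the main questions of the study.

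**Working it through.** There is no plan figure to reproduce. The sample of 25 is a convenience sample, given without effect size, SD, significance level or power. The check is to match the tests to the outcomes and then to illustrate the size of the problem.

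**1. Is there a paired yes/no outcome?**

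| Outcome (Methods) | Scale | Pre and post? | Yes/no as defined? |
|---|---|---|---|
| Range of motion (item 1) | continuous, goniometer | yes | no |
| Spasticity, MAS (item 1) | ordinal | yes | no |
| Finger-to-palm distance (item 2) | cm | yes | no |
| Pain, NRS or CNPI (item 3) | score | yes | no |
| Goal satisfaction (item 4) | scored response | final visit only | close to it, but no baseline value |
| Hand hygiene (item 5) | ordinal 0–3 | yes | no |
| Analgesics (item 6) | review | yes | no definition given |

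No row supplies a paired proportion.

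**2. What does ignoring the pairing cost?** With SD σ at each visit, correlation ρ and n patients, the standard error of the mean change is σ√(2(1−ρ)/n) if paired and σ√(2/n) if treated as independent. The ratio is 1/√(1−ρ), which is 1.20, 1.41 and 1.83 for ρ = 0.3, 0.5 and 0.7.

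Assume σ = 2, ρ = 0.5, n = 25 and a fall of 1.2 points:

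- paired SE = 2√(1/25) = 0.40, so the fall is 1.2/0.40 = 3.0 SEs;
- unpaired SE = 2√(2/25) = 0.566, so the fall is 1.2/0.566 = 2.12 SEs.

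For continuous normal scores at a two-sided 0.05 level, the noncentral t (24 df, noncentrality 3.0) gives paired power 0.82. The two-sample t-test on the same paired data gives 0.57 (40,000 simulated trials). Over standardised changes of 0.4 to 0.6 SD and correlations of 0.3 to 0.7, paired power is 0.37–0.96 and unpaired power 0.16–0.58.

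**3. The same on an integer 0–10 pain score.** Assumed: baseline mean 6.5, SD 2, fall 1.2, values rounded and clipped to 0–10, 25 pairs, 4,000 simulated trials per setting. High pain means a score at or above the cut, and McNemar's test is exact. At correlation 0.5:

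| Test | Power |
|---|---|
| Paired t | 0.788 |
| Wilcoxon signed-rank | 0.778 |
| Two-sample t | 0.543 |
| Rank sum | 0.517 |
| McNemar, cut 4 / 5 / 6 / 7 | 0.080 / 0.256 / 0.345 / 0.334 |

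With no true change, the two-sample t-test rejects in 0.6% of trials at correlation 0.5 and 0.2% at 0.7, against a nominal 5%. The paired t-test rejects in 5.1% and 5.2%.

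**4. The paired t-test with McNemar's test as fallback.** The protocol names no normality check, so a Shapiro-Wilk test at 0.05 is assumed. At correlation 0.5 it fires in 32% of trials if applied to the scores at either visit and in 19% if applied to the differences. Power of the two-step rule over both triggers and the four cuts:

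| Correlation | Paired t | Two-step rule | Loss (points) |
|---|---|---|---|
| 0.3 | 0.667 | 0.483–0.627 | 4–18 |
| 0.5 | 0.788 | 0.566–0.705 | 8–22 |
| 0.7 | 0.942 | 0.644–0.782 | 16–30 |

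**5. Hand hygiene.** There are C(28,3) = 3,276 ways to spread 25 patients over grades 0 to 3. Leaving out the four in which all patients share one grade, the largest Shapiro-Wilk p-value is 0.0095 (counts 4, 8, 9, 4). A check on the raw scores at 0.05 would therefore always send this outcome to McNemar's test, for which it has no cut-off.

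**The case against.** Four points can be made for the protocol.

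- **The analgesic review could be the intended proportion.** It is done at every visit and serves Objective 4, and needing an analgesic or not would be a natural paired yes/no outcome. That is a fair guess at the intention. But the protocol defines no such outcome, and the sentence applies the test to pre/post data generally. McNemar's test can be kept for this item once it is defined.
- **The last sentence may mean a comparison of change scores between groups of patients**, for instance those with and without a gain in motion. That would be a valid two-sample analysis. However, no groups are defined anywhere, and the sentence names two visits as what is compared. If a group comparison was meant, the groups must be stated.
- **The weight is limited.** The mixed models cover all key outcomes and respect the pairing, the study is an exploratory pilot, and the unpaired test errs towards too few rejections. All of this stands. Yet the sentence offered for judging statistical significance is the paired-test sentence, so the mixed models do not remove the conflict.
- **The illustration rests on assumptions.** The trigger, its level and the cut-offs are not in the protocol, and NRS pairs may number fewer than 25 because some patients are scored on the CNPI. This stands too: the percentages show direction and rough size, not the power of this study. The mismatch between tests and outcomes does not depend on them.

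**Conclusion.** The point holds, as something the protocol states wrongly rather than leaves open. The reference to proportions and the McNemar fallback fit none of the pre/post outcomes as defined, and the last sentence contradicts the within-patient design. Deleting the reference to proportions is enough to make the paired t-test runnable; the fallback and the last sentence need replacing.

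Under the assumed inputs, the unpaired route costs about 25 percentage points of power against the paired t-test (0.788 − 0.543 = 0.245), and the McNemar fallback about 8–22 points, or 4–30 over correlations of 0.3 to 0.7. No stated error rate or power is breached, because the protocol gives none. The damage is to clarity, and to protection against choosing the test or cut-off after the data are seen. It should be fixed, but it does not undermine the study, because the mixed models remain sound.

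**What to change.** Remove the reference to proportions and replace the test and fallback wording with, for example:

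> For each score, the mean within-patient change from baseline will be tested with a paired t-test and reported with a 95% confidence interval. The Wilcoxon signed-rank test will be used for ordinal scales (MAS, DAS), and for other scores if the within-patient differences are clearly non-normal. McNemar's test will be used only for a yes/no outcome defined in advance.

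State how clear non-normality will be judged, or fix the test for each outcome beforehand, so that the switch does not leave new discretion. If analgesic need is meant as a proportion, define it there.

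Replace the last sentence with:

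> Change in joint range or pain between two visits will be tested with these same paired tests.

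If a comparison between groups of patients was intended, name the groups instead. Keep the Spearman alternative to Pearson's correlation and the mixed models as planned. The cost is three or four sentences of statistical wording, with no extra data, visits or patients.

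### The rule for dropping the paired t-test checks normality of the outcomes, not of the within-patient differences, and so can discard a valid paired analysis for McNemar's test

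*Protocol*

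**What the plan says.** All of the rule stands in the protocol's Statistical Analysis section.

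- Main pre/post test: "a paired t-test on the difference of proportions, applicable to pre-treatment and post-treatment, will be performed".
- Trigger: "If normal distribution in the outcomes does not stand". Replacement: McNemar's test and, after a line break, "Spearman correlations will be calculated instead of paired t-test and Pearson's correlation, respectively". McNemar's test thus replaces the paired t-test, and Spearman replaces Pearson. No normality test, threshold or visit is named.
- Models: "We will employ repeated measures or linear mixed (multilevel) models of change to analyze within-person trajectories in all key outcomes", "with change indexed relative to everyone's own personal baseline". No fallback is attached to them.
- Correlation: "The correlation between range of motion and pain score will be reviewed by Pearson's correlation and or Spearman's rank correlation at single time point".

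Inclusion criterion 2 requires "Severe claw hand with less than 4 cm distance between the pulp of the fingers and palm of the hand", and criterion 3 requires MAS of at least 3. Under Methods, the same distance (in cm) and MAS are assessed at every visit. Criterion 4 asks for refractory pain but gives no score cut-off, and no criterion limits goniometer ROM.

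**The concern.** A paired t-test is a one-sample test on the differences (post minus pre). Its validity depends on how those differences are distributed, and the shape of the baseline or follow-up values does not enter. The protocol makes the outcomes themselves the condition, and two of them are cut at entry by the protocol's own criteria. The trigger can then respond to the entry criteria while the assumption it is meant to protect holds.

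At stake is which test supplies the reported p-value for a pre/post comparison. The named replacement is a test for paired binary data, so a needless switch also means dichotomising a measured scale at a cut-point that the protocol does not define.

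**Working it through.** The protocol gives no alpha, power, SD or effect size, and its 25 patients are a convenience sample, so there is no figure of its own to reproduce. The check is by simulation at n = 25. Shapiro-Wilk at 5% stands in for the unnamed normality check. All distributions below, and a top MAS grade of 4, are assumptions.

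**1. Baseline distance cut at 4 cm.** Parent population normal, kept only between 0 and 4 cm; within-patient differences N(1, 1); 4,000 studies per row.

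| Parent mean / SD (cm) | Baseline fails | Differences fail |
|---|---|---|
| 2 / 1 | 3% | 5% |
| 3 / 1.5 | 20% | 5% |
| 4 / 2 | 37% to 38% | 5% |
| 4 / 1.5 | 51% to 52% | 5% |

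The closer the population mean lies to the limit, the more often the check fails. The range is not a bound: parents of 5 / 2 and 6 / 2 gave 58% and 74% (3,000 studies each).

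**2. Is the t-test valid when the check fires?** With a uniform 0 to 4 cm baseline and normal change (mean 1, SD 0.7), a check on baseline or follow-up fires while the differences pass in 29% of studies. With the same set-up and no true change, the paired t-test rejects in 4.8%, which is its nominal level. Moving the check to the differences cuts firing from 31% to 5%. The limit acts at baseline only; follow-up values alone fail in 5%.

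**3. Baseline MAS.** With values confined to grades 3 and 4, the check fails in 100% of studies, whether 50%, 70% or 90% of patients are at grade 3. MAS changes are also whole or half grades: with change spread over 3 to 5 grades, the differences fail in roughly 94% to 100%.

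**4. Pain and ROM.** With no numeric entry limit there is nothing to truncate. ROM read in 5-degree steps from a normal population fails in 7%. NRS fails in 16% (mean 5, SD 2) to 69% (mean 8, SD 1.5), from whole-number scoring and the ceiling and not from the entry criteria.

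**5. Cost of a switch.** Assumed NRS example: baseline mean 6, SD 2; fall of mean 1.2, SD 2; scores rounded and kept within 0 to 10; n = 25. Power is about 0.83 for the paired t-test, 0.82 for the signed-rank test and 0.42 for McNemar's test on the score split at 4. Hand check for the t-test: standardised change 1.2 / 2 = 0.6; noncentrality 0.6 × √25 = 3.0 on 24 degrees of freedom; power 0.82. The McNemar figure moves with the cut: about 0.44 at 5 and 0.30 at 6. It is low because only patients who cross the cut count. An exact McNemar test needs at least six patients crossing, all in one direction (2 × 0.5⁶ = 0.031, against 2 × 0.5⁵ = 0.0625). This example measures the cost of the fallback; it does not show that entry limits trigger it for pain.

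**The case against.** **The word may mean change scores.** The section says that change is measured from each patient's own baseline, and diagnostics are commonly left to an SAP, which is not at hand. But the same section uses the word outcome for the measured variable and names change or improvement separately. The choice of normality test can wait for an SAP; the protocol has already stated which quantity decides. If differences were meant, the same sentence is needed to say so.

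**MAS is not a false alarm.** This stands. MAS differences fail almost as surely as MAS values, and a move away from the t-test is sensible for an ordinal score. The fault for MAS is the destination, McNemar's test.

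**Half of the clause is sound.** This also stands. Pearson or Spearman is applied to ROM and pain levels at one time point, and there it is reasonable to look at the variables themselves.

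**The larger fault is the choice of tests.** A paired t-test on proportions with McNemar's test as its fallback needs correction in its own right. Replacing McNemar alone, however, would leave the wrong trigger in place, though with little effect on power.

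Three stronger readings are tempting and are not supported:

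- *The entry criteria make the trigger fire in general.* This is certain only for baseline MAS. For distance it depends on an unknown population, and it does not apply to pain, the first objective, or to ROM.
- *The trigger overlooks departures that would harm the t-test.* A check on outcomes can miss non-normal differences: with half the patients falling 4 points and half 0, the t-test nevertheless keeps a level of about 4% to 5%. A level of 8.7% appeared only with strongly skewed differences assumed for the purpose (10% of patients around +36 degrees, 90% around −4, mean zero). Nothing in the protocol points to such a pattern.
- *Mixed-model residuals bear on this trigger.* The clause replaces only the paired t-test and Pearson's correlation, so the models are unaffected.

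**Conclusion.** The point holds in a limited form and is minor. For the paired comparisons the protocol conditions the choice of test on the wrong distribution. For distance, the entry limit can cause a needless switch: the baseline fails in about 3% to 52% of studies under the four populations tabulated, while normal differences fail in 5%. For baseline MAS failure is certain if only two grades are possible, but the differences fail as well. For pain and ROM the wrong quantity is still named, but the entry limits play no part.

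The cost lies in the fallback. Against McNemar's test the assumed pain example loses about half its power (0.83 to 0.42); against a paired rank test it loses about 0.01. These figures rest on assumed distributions and an assumed 5% Shapiro-Wilk check. That the paired t-test depends on the differences rests on no assumption.

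**What to change.** Replace the clause with, for example:

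*For paired comparisons of pain, ROM and distance, normality will be judged by plot on the within-patient differences, with the Wilcoxon signed-rank test as the fallback. For the ordinal MAS and hygiene scores the signed-rank test is used from the start. The choice between Pearson and Spearman is still judged on the two variables being correlated.*

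The last sentence is needed so that the sound half of the present clause is not lost. The signed-rank test is the paired one; it should not be confused with the rank sum test that the section names elsewhere, which compares independent groups.

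The cost is one short passage of protocol or SAP wording, best settled before the data are examined. No patient, visit or measurement changes.
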